7.9.3.4. Additional Dissection Specific Assessments

Additional dissection specific assessments include the following:

- Coverage of primary entry tear (exclusion of false lumen)
- Extension of dissection (proximally or distally) with or without complications
- Continuing or new false lumen (FL) perfusion
 - Primary intimal tear false lumen perfusion (PIT FLP)
 - Proximal aorta false lumen perfusion (PA FLP)
 - Distal aorta false lumen perfusion (DA FLP)
 - Proximal branch false lumen perfusion (PB FLP)
 - Distal branch false lumen perfusion (DB FLP)
- Aortic remodeling post-procedure as measured by:
 - o Change from baseline* in the maximum true lumen (TL) diameter over the length of the stent graft
 - Change from baseline* in the maximum false lumen (FL) diameter over the length of the stent graft
 - o Change from baseline* in the maximum total descending thoracic aortic diameter
 - FL thrombosis over the length of the stent graft
 - * The discharge computerized tomography angiogram (CTA) will be used as the baseline to assess aortic changes. If a discharge CTA is not performed then, the one month follow-up CTA will be used for baseline purposes.

The rate of the above endpoints will be calculated at the post-operative time point and at each scheduled follow-up and the calculation will be based on the number of subjects who had the event divided by number of implanted subjects under the Dissection indication who are evaluated for that event at the time point. The imaging endpoint analysis time window will be used to determine if an image assessment belongs to a respective time point and the reporting details can be found in section 7.2.3 (Table 1).

Thoracic dissection measurement over entire DTA and thoracic measures over endograft segment

If there are multiple images in a reporting window, the image with the largest maximum thoracic aortic centerline diameter over the entire DTA in the window will be used for reporting all related measurements (e.g., maximum thoracic aortic centerline diameter, maximum true lumen diameter, etc.)

7.9.3.5. Endoleaks

Type of endoleak includes Ia, Ib, Ic, type I combined, II, III, IV, and undetermined. The rate of these events will be reported for the 30-days visit, 6-month visit and at each annual follow-up and will be reported as the composite rate of endoleak requiring intervention or endoleak observed by imaging

VML_Eval Statistical Analysis Plan **Form** Medtronic Revision [6.0] Page 24 of 27

assessment. The endpoint will be analyzed using the core lab imaging assessment and the site reported imaging assessment, separately.

The endpoint will be reported descriptively with frequency counts and percentages for any endoleak as well as by type.

- The numerator will include all subjects having endoleak requiring intervention within the analysis time window or any endoleak reported on imaging assessment within the time window.
- The denominator will include all subjects having endoleak requiring intervention within the analysis time window or having evaluable imaging assessment within the time window.

For imaging assessment, any endoleak reported during the time window will be accounted for in analysis. The secondary procedure date will be used as the basis of determining if an endoleak requiring intervention occurred within the time window.

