7.2.2. Duration of Follow-up

If a subject is not expired, then duration of follow-up will be calculated from the last date of follow-up visit or the final assessment as indicated on the Study Exit CRF, whichever is later. If a subject is expired, then the duration of follow-up will be calculated using the date of death. If a subject withdraws from the study, the duration of follow-up will be calculated using the date of withdrawal. Data except death, if any, reported after the date of withdrawal will be excluded from reporting.

Time Window of an Event or Assessment 7.2.3.

For events that can occur or are observed at any time during the study, such as an adverse event or death, no time window will be applied. For other events, an event that occurs "within 1 month" is an event that takes place between Days 0 to 30, inclusive. Similarly, an event that occurs "within 1 year" is an event occurring between Day 0 to Day 365, inclusive.

For visit-related or imaging based assessments, such as a CT scan, MRI, X-Rays, the analysis windows presented in Table 1 will be applied for by-visit data summaries:

Revision [6.0]

Page 15 of 27

Table 1. Time Window for Imaging Observations Analysis

Study Visit	Target Day	Scheduled Follow-Up Window	Analysis Window for Imaging Observations
Implant	0	Day 0	0
Discharge	n/a	n/a	1-14 Days
1 Month	30	15-45 Days	15-122 Days
6 Months	183	153-239 Days	123-270 Days
12 Months	365	335-421 Days	271-480 Days
24 Months	730	674-842 Days	481-913 Days
36 Months	1095	1039-1207 Days	914-1278 Days
48 Months	1460	1404-1572 Days	1279-1644 Days
60 Months	1825	1769-1937 Days	1645-2008 Days

Imaging based analyses will follow a "worst case" principle where any 'positive' finding of an undesirable outcome (e.g., fracture) or the worst measure (e.g., aneurysm diameter) in the analysis window will be used. If there are 2 or more assessments of the same subject for the same type of event within the same time window, then the following rules are applied:

- 1. If there are 2 or more positive findings on evaluable images for the same type of event for the same subject in the window, the earliest image showing a positive finding will be used to determine that the subject had an event in the window and this subject is only counted once for this type of event in this window.
- 2. If there is no positive finding for the event, the latest evaluable image showing no event will be used for analysis.

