7.9.3.2. Aneurysm Diameter Changes

Aneurysm Diameter change will be calculated based on the maximum measurable aneurysm diameter during the post-operative follow-up and each annual follow-up. Reference diameter is the diameter measured at first post-operative follow-up through 1 month. Change of aneurysm diameter will be defined as 1) "increased" if an aneurysm growth is strictly greater than 5 mm of the maximum measurable aneurysm diameter; 2) "decreased" when an aneurysm becomes strictly smaller in size by more than 5 mm; 3) "no change" when the change is within 5 mm.

[figure not shown]
Aneurysm diameter change rates will be calculated separately for increase, decrease and no change based on the number of subjects who had the event divided by number of implanted subjects who are evaluated for aneurysm diameter change at the time point. The analysis time window will be used to determine if an image assessment belongs to a respective time point. The analysis time window for each time point is given in Section 7.2.3.

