7.9.3.3. Exclusion of Thoracic Lesions

Rate of exclusion of thoracic lesions will be reported for 1-month, 6-month and each annual follow-up. The endpoints may be analyzed using site-reported imaging assessments or core lab reported imaging assessments, separately.

Revision [6.0]

Page 21 of 27

Exclusion of Aneurysm

Exclusion of Aneurysm is defined as the absence of a type I or III endoleak associated with the absence of growth of > 5 mm of the maximum measurable aneurysm diameter; reference diameter is the diameter measured at first post-operative imaging exam.

Rate of Exclusion of Aneurysm will be calculated for each scheduled follow-up and the calculation will be based on the number of subjects who had the event divided by number of implanted subjects that are evaluated for that event at the time point. Imaging endpoint analysis time windows will be used to determine if an image assessment belongs to a respective time point. The reporting details can be found in Section 7.2.3 (Table 1).

The endpoint will be derived as follows:

- Subjects having a Type I or III endoleak or having aneurysm growth > 5mm will be considered as failures of the endpoint [defined as k].
- Otherwise subjects without a failure event and having evaluable imaging for both endoleak and aneurysm growth will be considered as a success (i.e. Exclusion of the aneurysm) [defind as m].
- Subjects without a type I or III endoleak and without aneurysm growth > 5mm, but missing one or both imaging assessments will be excluded from the analysis.

The rate will be calculated as m/(m+k), where the numerator will consist of all subjects having success for exclusion of the aneurysm [m]. The denominator will consist of all subjects having exclusion [m] or subjects having a failure event [k].

[figure not shown]
The endoleak component will be derived according to Section 7.9.3.5.

The aneurysm growth component is based on the calculated difference between the assessments at follow-up minus the first post-operative assessment. Subjects must have the maximum aneurysm diameter reported at both the post-operative assessment and the follow-up assessment. If the subject is missing either the post-operative and/or follow-up assessment, the subject is considered to have missing data for this component. The post-operative image can be either at 1 month follow-up or discharge. At each follow-up the largest aneurysm diameter will be used in the calculation of aneurysm diameter change from baseline.

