7.9.3.6. Technical Observations

A technical observation is defined as a defect, malfunction, or failure of the device. Also, this may pertain to the device or system not functioning according to its designed intent. These might include (but are not be limited to) stent fracture, migrations, and device access difficulties. Technical observations may or may not be related to an adverse event in a subject.

Technical observations that are not associated with any untoward medical occurrence in a subject will be reported on the Imaging Exam Forms, Index Endovascular Procedure Form or Secondary Procedure Form. Technical observations that result in an Adverse Event will be considered by definition as Adverse Device effects and must also be documented in an Adverse Event form.

Technical observations may be analyzed using site-reported imaging assessments or core lab reported imaging assessments, separately.

Rate of Non-recurrent Imaging Endpoints

The following imaging assessments will be identified and reported by investigators per protocol definition - once such an event is discovered through an imaging assessment, it will likely stay noticeable on the subsequent imaging assessments at all follow-ups:

- Stent graft migration
- Stent graft separation
- Stent graft kinking
- Stent graft twisting
- Loss of stent graft integrity

Revision [6.0]

Page 25 of 27

The rate of these events will be reported for the 30-day visit, 6-month visit and for each annual followup and calculated based on the number of subjects who had the event divided by the number of implanted subjects who are evaluated for that event at the time point. The imaging endpoint analysis time window will be used to determine that an image assessment belongs to a respective time point and the reporting details can be found in section 7.2.3.

Further, if such event is observed during a time window, it will most likely be observed on all the images thereafter (if the imaging visit is completed); hence only the first observed event will be used to calculate the event rate - once one such event is reported for a subject for a time point, that subject will be excluded from that event rate reporting for that same event term for any later time points.

More detailed programming rules are described below:

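### SAP 7.9.3.6 rule a, read literally, drops a persistent device finding first imaged before Day 15 from every reported rate; 7.9.3.5 leaves the window for early endoleak re-interventions unstated

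*SAP*

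**What the plan says.** Table 1 (SAP 7.2.3) gives consecutive imaging windows: Implant is Day 0, Discharge is Days 1-14, and 1 Month is Days 15-122. The same section has a separate rule for dated events: one that occurs within 1 month "is an event that takes place between Days 0 to 30, inclusive".

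For non-recurrent imaging findings (migration, separation, kinking, twisting, loss of integrity), SAP 7.9.3.6 states: "The rate of these events will be reported for the 30-day visit, 6-month visit and for each annual followup". It refers to 7.2.3 for the windows. On exclusion, the running text says: "once one such event is reported for a subject for a time point, that subject will be excluded from that event rate reporting". Programming rule a, lower in the same section, takes the earliest positive image, assigns it to its visit window, counts it for that visit, and takes the subject out of numerator and denominator at every visit after that.

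For endoleaks, SAP 7.9.3.5 has the same visit list ("The rate of these events will be reported for the 30-days visit, 6-month visit and at each annual follow-up"). It combines leaks seen on imaging with leaks that needed intervention. Interventions are dated as follows: "The secondary procedure date will be used as the basis of determining if an endoleak requiring intervention occurred within the time window". The denominator follows suit: "The denominator will include all subjects having endoleak requiring intervention within the analysis time window or having evaluable imaging assessment within the time window". SAP 7.9.3.3 uses this result for Exclusion of Aneurysm: "The endoleak component will be derived according to Section 7.9.3.5".

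**The concern.** The study is meant to describe the device acutely as well as at 30 days (SAP 3 and 4.1), and 4.3.3 has the additional observations evaluated through the 30 day visit. Discharge has an analysis window but does not appear in the visit lists of 7.9.3.5 and 7.9.3.6. The dissection endpoints in 7.9.3.3 and 7.9.3.4, by contrast, do get a post-operative time point.

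For findings that come and go, this only means that one time point is not tabulated. For non-recurrent findings it is worse, because rule a uses the first positive image to close the subject's record for that event. If that image falls in an untabulated window, the record is closed before anything has been counted. A kink visible on every scan for five years could be missing from every kink rate. That would also defeat the worst-case imaging principle added in SAP revision 6.0.

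The window for re-interventions raises a smaller question of the same kind: two programmers could place a Day 10 re-intervention for endoleak differently.

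**Working it through.** The plan gives no event rate or sample size calculation on which this depends, so there is no figure to reproduce. The check is to run the stated rules on test cases and then show the scale with assumed counts.

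**Inputs.** Windows: Table 1, contiguous from Day 0 to Day 2008. Reported visits: 1, 6, 12, 24, 36, 48 and 60 months (7.9.3.5, 7.9.3.6). Maximum enrolment: 44 (SAP 6). Interval method: exact binomial, as the SAP uses for its event rates.

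**Rule a, literal reading**

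| First positive image (still positive later) | Window assigned | Reported? | 1 to 60 months |
|---|---|---|---|
| Day 5 | Discharge | No | Excluded at all seven visits |
| Day 14 | Discharge | No | Excluded at all seven visits |
| Day 15 | 1 Month | Yes | Counted at 1 month, excluded afterwards |

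One day's difference in the first scan decides whether a persistent finding is counted once or never. A positive Day 0 image behaves like Day 5, because Implant is not a reported visit either.

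**Rule a against the running text.** The running text makes exclusion follow from the event having been reported for a time point. On that wording the Day 5 subject would not yet be excluded and would be counted at 1 month. Rule a has no such condition. The two give different results for the same subject.

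**Scale (assumed: all 44 subjects imaged, k with a persistent finding first seen on Days 1-14).** With zero events the exact upper limit is 1 - 0.025^(1/n). For n = 43 this is 1 - 0.025^(1/43) = 8.2%.

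| k | Literal rule a at 1 month | Each finding counted once |
|---|---|---|
| 1 | 0/43, 0-8.2% | 1/44 = 2.3% (0.1-12.0%) |
| 3 | 0/41, 0-8.6% | 3/44 = 6.8% (1.4-18.7%) |
| 5 | 0/39, 0-9.0% | 5/44 = 11.4% (3.8-24.6%) |

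**Endoleak re-interventions.** Section 7.9.3.5 refers to an analysis time window without naming it. Section 7.9.3.2 says of the same phrase: "The analysis time window for each time point is given in Section 7.2.3". But 7.2.3 holds both Table 1 and the Days 0-30 event rule.

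| Date of re-intervention | Under Table 1 | Under Days 0-30 |
|---|---|---|
| Day 10 | Discharge: in no endoleak rate | Counted at 1 month |
| Day 16 | Counted at 1 month | Counted at 1 month |

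Under Table 1, a Day 10 subject with a clean scan on Days 15-122 counts as free of endoleak at 1 month. Without an evaluable scan in that window the subject leaves both numerator and denominator.

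**Endoleak on imaging.** A leak seen on Day 5 and absent on Days 30, 183 and 365 is negative at 1, 6 and 12 months. It is positive only in Discharge, which is not tabulated.

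**The case against.** Rule a also says that the event is to be included in the rate for its corresponding visit. A programmer who obeys the whole sentence must either show the event at Discharge or, following the running text, hold back the exclusion, so losing the event means following half the rule. This stands to the extent that the outcome is not certain. It does not remove the problem: the first route needs a Discharge rate that 7.9.3.6 does not list, and the second needs the running text to override a rule presented as the more detailed one.

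On re-interventions, Table 1 is stated to apply to visit-related or imaging-based assessments, and the cross-reference in 7.9.3.2 concerns diameter images. The Days 0-30 reading is therefore open. That is correct, and it is why this part is a question of missing definition.

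A reader might infer that the 30-day endoleak rate is biased in the device's favour. The documents do not support that. It is a by-visit rate, and a leak gone by the 1-month scan is rightly absent from it. Nor do they establish an overstated Exclusion of Aneurysm rate: any effect depends on the Table 1 reading, and a subject whose early leak was treated and whose later scan is clean arguably meets the definition at that visit.

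Early events also have other outlets: secondary procedures (7.9.3.1, and 4.3.3 for Type I/III endoleaks), adverse events for Days 0-30, and the listing of malfunctions and failures (7.10). These limit the harm but do not supply the missing finding-specific rates.

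**Conclusion.** Rule a is wrong as written. It conflicts with the running text of its own section, and one literal execution leaves a persistent migration, separation, kink, twist or integrity loss first imaged before Day 15 out of every reported rate. It would be too strong to say that the plan certainly deletes such findings, since the running text allows a reading that keeps them.

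The endoleak points are cheap improvements. The window for re-interventions is undefined, and under Table 1 it would count Day 16 but not Day 10. Leaks seen only on Days 1-14 are shown at no time point, which is a gap in reporting and not an error in the 30-day rate.

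The real size is unknown. Every count above is assumed, and having all 44 subjects imaged early is a convenience: the SAP allows for no discharge CTA (4.3.3 footnote), and only contrast CTA or MR is evaluable for endoleak (Table 2). The available protocol copy carries only page headers, so the discharge imaging schedule could not be checked. No effect on the primary safety observation or Treatment Success is shown.

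**What to change.** 1. Amend rule a in 7.9.3.6 so that a subject leaves later visits only after the event has been counted at a reported time point, and so that an early finding still visible later is otherwise counted at the first reported visit.
2. Add Discharge (Days 1-14) as a reported time point for the 7.9.3.6 non-recurrent findings and for image-based endoleak, with its own denominator of subjects with evaluable images. Keep Days 15-122 for the 1-month imaging rate. A persistent finding is then counted at Discharge, and a following 0/43 at 1 month is legitimate. Without this column, item 1 alone would count it at 1 month.
3. In 7.9.3.5, state that the first window for endoleak requiring intervention starts at Day 0, and where it ends. The existing denominator rule keeps numerator and denominator matched. State in 7.9.3.3 whether this carries into the endoleak component of Exclusion of Aneurysm and PAU.

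The cost is a few sentences in three SAP sections, one windowing rule and one extra table column, all from data already collected. The downside is that early rates may look slightly less favourable and the Discharge denominator may be small.

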7.9.3.6. Technical Observations

A technical observation is defined as a defect, malfunction, or failure of the device. Also, this may pertain to the device or system not functioning according to its designed intent. These might include (but are not be limited to) stent fracture, migrations, and device access difficulties. Technical observations may or may not be related to an adverse event in a subject.

Technical observations that are not associated with any untoward medical occurrence in a subject will be reported on the Imaging Exam Forms, Index Endovascular Procedure Form or Secondary Procedure Form. Technical observations that result in an Adverse Event will be considered by definition as Adverse Device effects and must also be documented in an Adverse Event form.

Technical observations may be analyzed using site-reported imaging assessments or core lab reported imaging assessments, separately.

Rate of Non-recurrent Imaging Endpoints

The following imaging assessments will be identified and reported by investigators per protocol definition - once such an event is discovered through an imaging assessment, it will likely stay noticeable on the subsequent imaging assessments at all follow-ups:

- Stent graft migration
- Stent graft separation
- Stent graft kinking
- Stent graft twisting
- Loss of stent graft integrity

Revision [6.0]

Page 25 of 27

The rate of these events will be reported for the 30-day visit, 6-month visit and for each annual followup and calculated based on the number of subjects who had the event divided by the number of implanted subjects who are evaluated for that event at the time point. The imaging endpoint analysis time window will be used to determine that an image assessment belongs to a respective time point and the reporting details can be found in section 7.2.3.

Further, if such event is observed during a time window, it will most likely be observed on all the images thereafter (if the imaging visit is completed); hence only the first observed event will be used to calculate the event rate - once one such event is reported for a subject for a time point, that subject will be excluded from that event rate reporting for that same event term for any later time points.

More detailed programming rules are described below:

- a. If at least one positive (event) imaging assessment is found for an event type (e.g., fracture) - select the earliest positive assessment and then apply the visit window rules: The event will be included in the rate calculation for the corresponding visit, and for any visit after this one, that patient will be excluded from both the numerator and denominator of the event rate calculation;
- b. If no positive imaging assessment is found, select the one using the 'latest evaluable image showing no event in the window rule';
- c. Steps a and b need to be repeated for each specific event, such that a different image may be used for reporting each event type.
- d. These observations will be assessed separately, for example, if a patient is determined to have fracture at 1-month, that patient will be excluded from fracture rate calculation for the visits after 1-month, but if no data support that the same patient has migration or kinking at 1-month, that patient will be included in the rate calculation at the later visit if the data are available until the relevant event(s) is/are determined.

Rate of Recurrent Imaging Observations

The following imaging assessments will be identified and reported by investigators per protocol definition; these events may appear or disappear through the imaging assessment from time to time:

Loss of stent graft patency

More detailed programming rules are described below:

- Slot all non-missing (evaluable) imaging assessments into the correspondent reporting
- b. If multiple imaging assessments are found within the same visit window:
 - i. If there is any positive finding for the event on evaluable images in the window, select the earliest image showing a positive finding e);
 - ii. If there is no positive finding for the event, select the latest evaluable image showing no event.

VML_Eval Statistical Analysis Plan **Form** Medtronic Revision [6.0] Page 26 of 27

Similar rules will be applied for the aortic artery measurement (such as diameter and length, etc.) during the follow-up visits.

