4.3.1. Primary Safety Observation

The following clinical outcomes will be collected for reporting. The initial reporting period will be all occurrences within 1 month (Day 0 - Day 30) from the index procedure. The outcome data will consist of:

- Aorta-Related Mortality
- Stroke
- Paraplegia
- Left Arm/Hand Ischemia

Primary Effectiveness Observation 4.3.2.

The primary effectiveness observation is treatment success (defined below) and will be captured within the initial reporting period of 1 month from the index procedure.

Treatment success is defined as:

Technical success, which is the successful delivery and deployment of the stent graft (deployment of the Valiant Mona LSA Thoracic Stent Graft System in the planned location with no unintentional coverage of other vessels, assessed intra-operatively, and the removal of the delivery system) and successful exclusion of the aneurysm/penetrating ulcer or primary entry tear while maintaining patency of the MSG and BSG at 30 day visit.

Additional Observations 4.3.3.

The following additional observations will be evaluated through the 30 day visit and at each follow up visit.

Major adverse events (MAEs) rates within 30 days of the initial or secondary procedures, including:

Form Medtronic

Revision [6.0]

Page 7 of 27

- All-Cause Mortality
- Myocardial Infarction
- Paraplegia
- Renal Failure
- Stroke
- Left Arm/Hand Ischemia
- Secondary endovascular procedures
- Secondary endovascular procedures for primary device failures (including Type I/III endoleaks, aneurysm expansion, aneurysm/aortic rupture, and BSG occlusion)
- Rupture
- **Endoleaks**
- Maximum aneurysm diameter change from baseline*
- Exclusion of aneurysm
- Exclusion of penetrating aortic ulcer (PAU)
- Stent graft patency
- Stent graft integrity
- Conversion to surgery
- Surgical revascularization of the LSA
- **Paraparesis**
- Adverse events including serious adverse events and device, procedure, and/or disease-related Adverse Events
- For CTBD, these additional observations will be evaluated:
 - Coverage of primary entry tear (exclusion of false lumen)
 - Extension of dissection (proximally or distally) with or without complications
 - Continuing or new false lumen (FL) perfusion
 - Primary intimal tear false lumen perfusion (PIT FLP)
 - Proximal aorta false lumen perfusion (PA FLP)
 - Distal aorta false lumen perfusion (DA FLP)
 - Proximal branch false lumen perfusion (PB FLP)
 - Distal branch false lumen perfusion (DB FLP)

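### Read literally, the counting rule for lasting device defects leaves a defect first seen on Days 0-14 out of every planned rate; another sentence in the same section allows a different reading, and the SAP does not choose

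*SAP*

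**What the plan says.** SAP 7.9.3.6 (Technical Observations, non-recurrent imaging endpoints) covers five device findings: migration, separation, kinking, twisting and loss of integrity. On timing it says "The rate of these events will be reported for the 30-day visit, 6-month visit and for each annual followup". Images are placed in visits by the windows of SAP 7.2.3, where "the analysis windows presented in Table 1 will be applied for by-visit data summaries". In Table 1 of that section the imaging windows begin with Implant (Day 0), Discharge (Days 1-14) and 1 Month (Days 15-122).

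Two parts of 7.9.3.6 govern counting:

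- The narrative paragraph says "hence only the first observed event will be used to calculate the event rate" and then "once one such event is reported for a subject for a time point, that subject will be excluded from that event rate reporting", the exclusion applying to later time points.
- Rule a selects the earliest positive image, applies the windows to it, and continues: "The event will be included in the rate calculation for the corresponding visit, and for any visit after this one, that patient will be excluded". The exclusion covers both numerator and denominator.

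Three other places bear on the point:

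- SAP 4.3.3, whose list includes stent graft integrity, says "The following additional observations will be evaluated through the 30 day visit and at each follow up visit".
- SAP 7.9.3.4 does give the dissection endpoints an early rate: "The rate of the above endpoints will be calculated at the post-operative time point and at each scheduled follow-up".
- SAP 7.9.3.3 shows that discharge images are foreseen: "The post-operative image can be either at 1 month follow-up or discharge". The baseline footnote in 4.3.3 prefers the discharge CTA, but allows that it may not be done.

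**The concern.** Rule a has two halves: count the event at its own visit, then remove the subject from later visits. For a finding whose earliest positive image falls on Days 0-14, the first half has no planned rate in which to act. Read literally, the second half still acts. The subject leaves the 30-day and all later rates without having been counted in any of them, even if the defect is visible on the 1-month image.

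Whether a defect counts would then depend on when it was first imaged. A kink first seen on Day 10 enters no rate; the same kink first seen on Day 30 enters the 30-day rate. Since some subjects may have no discharge CTA, the two situations can arise side by side in one table. These are device-performance rates, and SAP 4.2 says the data may be used for marketing applications.

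**Working it through.** The documents state no figure on this point, so there is nothing to reproduce. The check is a trace through the rules, followed by an illustration.

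**Inputs.** Windows: Table 1 in SAP 7.2.3. Planned rates: 7.9.3.6, giving 1, 6, 12, 24, 36, 48 and 60 months (seven rates). Counting rule: 7.9.3.6, rule a. Maximum enrolment: 44 (SAP section 6).

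**Trace under the literal rule.** The Table 1 imaging windows cover Days 0-2008 without a gap.

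| Earliest positive image | Window | Planned rates that count it | Later planned visits |
|---|---|---|---|
| Day 0 | Implant | 0 of 7 | excluded from all 7 |
| Days 1-14 | Discharge | 0 of 7 | excluded from all 7 |
| Days 15-122 | 1 Month | 1 of 7 | excluded from the other 6 |
| Day 123 to Day 2008 | 6 Months or later | 1 of 7 | excluded from any that follow |

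The Day 0 row matters only if an imaging type listed in Table 2 is used on that day.

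**Direction.** Let n be the other subjects evaluable at 30 days, x their events, and k the subjects whose early defect is still visible at 1 month. The literal rule gives x/n; counting the early defects gives (x+k)/(n+k). The difference is

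(x+k)/(n+k) − x/n = k(n−x)/[n(n+k)] ≥ 0.

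So the literal rule can lower the 30-day rate or leave it unchanged, but cannot raise it.

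**Illustration.** Assume all 44 subjects are imaged at discharge and at every visit, early defects persist, and no new ones appear by Day 122. The documents give no frequency of discharge imaging or of early positives, so k is an assumption.

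| k | Literal rule, 30-day rate (exact 95% CI) | Persisting defect counted at 1 month (exact 95% CI) |
|---|---|---|
| 0 | 0/44 = 0.0% | 0/44 = 0.0% |
| 1 | 0/43 = 0.0% (0 to 8.2%) | 1/44 = 2.3% (0.1 to 12.0%) |
| 2 | 0/42 = 0.0% (0 to 8.4%) | 2/44 = 4.5% (0.6 to 15.5%) |
| 3 | 0/41 = 0.0% (0 to 8.6%) | 3/44 = 6.8% (1.4 to 18.7%) |

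The intervals overlap widely. What changes is whether the table shows a defect at all.

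**The two readings side by side.** Rule a excludes the subject from any visit after the one in whose window the earliest positive falls; it does not ask whether that visit has a rate. The narrative paragraph excludes once the event has been reported for a time point, and the only reported time points are the seven above. On that wording a discharge finding triggers no exclusion, and a persisting defect counts at 1 month. But the same paragraph also restricts the rate to the first observed event, which agrees with rule a. The text supports both programs, and they give different 30-day rates whenever k is above zero.

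**The case against.** The strongest reply is that the loss is only one reading. Rule a elaborates the narrative paragraph, which ties exclusion to reporting. Rule a itself joins counting to exclusion, so it is not obvious that the second half should run where the first cannot. The wording in 4.3.3 also suggests cumulative capture up to the 30-day visit, and the accountability table in 7.1.1.2 runs from Implant straight to 1-Month. This stands: a reader might infer that the SAP definitely drops these events, and the documents do not support that certainty. It does not remove the point, because rule a is the programming instruction and its literal application does lose the event.

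A reader might also infer that early device failures would be concealed. That goes too far. SAP 7.9.3.6 defines a technical observation as a device defect, malfunction or failure, and SAP 7.10 lists malfunctions and failures. The case should therefore appear in a listing, and in the adverse event summaries if it caused an event. A listing is not a rate, but in a descriptive study of up to 44 subjects it discloses the case.

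Two further limits stand. The five findings follow protocol definitions that are not readable in the supplied text, and a definition that needs change from a first post-operative image could not be met on that image. Revision 6.0 also draws its imaging rules from a sponsor work instruction that is not supplied and may deal with discharge images.

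**Conclusion.** The point holds as an unresolved rule with a one-sided consequence. Applied literally, rule a with Table 1 leaves a non-recurrent device finding first imaged on Days 0-14 out of all seven planned rates. The narrative paragraph supports a second reading under which a persisting finding counts at 1 month. The SAP does not decide between them.

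Under the literal rule any error favours the device. One persisting early defect among 44 fully imaged subjects moves the 30-day rate by 2.3 percentage points (0/43 against 1/44). That size rests on assumed imaging and persistence; the true frequency is unknown and may be zero. No primary observation is affected, and the point covers only findings that can be judged on an early image. Severity is minor to moderate; confidence is moderate.

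**What to change.** In SAP 7.9.3.6, for these five endpoints:

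1. Add a Discharge row (Days 0-14). Its numerator is subjects with an early event; its denominator is all subjects with an evaluable image on Days 0-14.
2. Amend rule a and the narrative paragraph to state: *Exclusion from later visits starts only after the event has been counted in a reported rate.*
3. Label the later rows as new events among subjects without a previously reported event.

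In the illustration with k = 1, the table would then show 1/44 = 2.3% at Discharge and 0/43 new events at 30 days. If only 22 of the 44 were imaged early, it would show 1/22 = 4.5%, then 0/43.

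Negative images from Days 0-14 should not be pooled into the 30-day denominator. That would depart from the Day 15-122 window and from the 7.9.3.6 denominator of subjects evaluated at the time point, and it can lower the rate. For example, suppose 30 subjects are imaged on Days 15-122 with 2 new positives, and 14 are imaged only at discharge, all negative. Pooling turns 2/30 = 6.7% into 2/44 = 4.5%.

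The cost is two or three SAP sentences, a small programming change on data already collected, and one extra table row whose denominator may be small.
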